Anorexia nervosa and bulimia nervosa are serious mental illnesses associated with significant morbidity and high relapse rates. AN has the highest mortality rate of any psychiatric illness. Although family-based treatment has led to improved outcomes for adolescent patients, this therapeutic approach has only limited utility in adults. Research suggests that patients with EDs are at greatest risk for relapse in the first six month following discharge from an intensive treatment (e.g. hospitalization or residential). Adjunct, supportive approaches delivered at these high risk times have potential to

improve eating disorder relapse prevention. Adjunct interventions also have potential to promote treatment engagement (attendance, compliance with meal plan, etc.) in patients with high ambivalence.

Project Heal® is a non-profit organization whose primary missions are providing grant funding for individuals with eating disorders who otherwise cannot afford treatment and promoting eating disorder recovery through campaigns and community programming. Project Heal has community sites (aka “chapters”) in 40 cities across the US and Canada. Project Heal recently launched a mentorship-based intervention at 12 of its sites, in which eligible individuals with eating disorders who are receiving treatment from a licensed professional are partnered for six months with peer mentors (individuals who have previously recovered from an eating disorder and who have participated in a general orientation/training program regarding the role of mentor). “Sites” refer to locations across the US and internationally where one or more individuals has established a local Project HEAL chapter. Chapters/“sites” range in size from just a few people to over 50. The Project HEAL national organization has ongoing contact with its sites about many different topics, including the Communities of HEALing program. In the past year, 12 sites have established Communities of HEALing programs, meaning that trained mentors carry out peer mentorship and free community support groups with oversight from a National-level Program Director. As more and more sites established peer mentorship programs, Project HEAL asked us to help them evaluate this intervention.

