Aim 2: Evaluate the impact of intervention condition on eating disorder symptoms. Hyp 2a. Participants in peer mentorship will have greater reductions in eating disorder symptoms, measured using the Eating Disorder Symptom Inventory (EPSI), compared to both control conditions. Hyp2b: For individuals who meet criteria for current or past anorexia nervosa, individuals assigned to peer mentorship will be more likely to achieve or maintain a BMI ≥ 18.5 , compared to both control conditions. Hyp2c: For individuals who meet criteria for current or past bulimia nervosa or binge eating disorder, individuals assigned to peer mentorship will be more likely to abstain from bingeing/purging and bingeing episodes, respectively, compared to individuals in either control condition.

Aim 3: Evaluate the impact of intervention condition on total cost for eating disorder treatment. Hyp 3. Estimated total cost for eating disorder treatment, measured using the Healthcare Utilization Survey, will be lower among peer mentorship participants compared to both control groups at (i) post-treatment and (ii) one-year follow up.

Exploratory Aim: Evaluate characteristics of individuals participating as peer and social support mentors. Exploratory hypothesis: Mentor characteristics and similarity between mentee and mentor characteristics will not influence mentee outcomes (acceptability, eating disorder symptoms, and estimated treatment cost).

Inclusion/Exclusion Criteria

This section details your study sample(s) and addresses the requirement for risk minimization. You may choose to divide your sample by population (healthy controls vs. subjects) or by procedure (subjects who will have an MRI) and then define different sets of criteria for each.

For each sample, create or insert a table to describe detailed criteria for study inclusion and exclusion and the method you will use to ascertain each criterion. The method of ascertainment may describe tests, scales and instruments. When relevant, indicate the level of training of the person who will make the assessment (e.g. clinical interview by a psychiatrist).

Inclusion/Exclusion Criteria needs to be numbered and listed in outline form (see Table template below)

Mentees (Adolescents or adults with anorexia nervosa, bulimia nervosa, or binge eating disorder):

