**Note that all EDRU screens will be reviewed with a clinician (MD or PhD level) and if any criteria are in question, the clinician will speak directly with the potential participant by telephone.*

CRITERION	METHOD OF ASCERTAINMENT
Inclusion:	
1. Ages 14 – 45 years	Initial telephone interview with Project HEAL staff, confirmation during telephone screening with EDRU research team member (RA level or higher)*
2. Meets criteria for current or past anorexia nervosa, bulimia nervosa , or binge eating disorder (criteria met either presently or at time of entry into treatment for most recent treatment course)	Eating Disorder Assessment -5 (administered by EDRU RA* during telephone screening)
3. Recent (within past 6 m) discharge from inpatient, residential, or partial hospitalization program (PHP)	Initial telephone interview with Project Heal staff, confirmation during telephone screening with EDRU RA*
4. Involved in outpatient treatment at an appropriate level of care	Telephone screening with EDRU RA* and Documentation from primary outpatient clinical provider using Provider Form
5. Medical stability	Telephone screening with EDRU RA* and Documentation from primary outpatient clinical provider using Provider Form
6. Access to Smart Phone or computer to complete study assessments	Telephone screening
Exclusion:	
1. Evidence of needing specialized treatment for another medical or mental health condition or substance use	Telephone screening with EDRU RA*

Mentors:

Mentors in the peer-mentorship group are adults who have recovered from an eating disorder, while mentors in the social support group are adults who never had an eating disorder. All mentors are individuals recruited and trained by Project Heal to do volunteer work within their organization.

Inclusion/Exclusion criteria:

CRITERIA	METHOD OF ASCERTAINMENT
Inclusion	
1. Participating as a peer or social support mentor in Project HEAL intervention	1. Weekly telephone supervision with mentors
Exclusion	
1. Not being a mentor	1. Same as above

Study Procedures

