Cover page

Official Title: Evaluation of the Communities of HEALing mentorship/support group program:
Assessment of preliminary efficacy

NCT number: NCT03317379

Document date: 3/23/2018

Statistical Analysis Plan

Intent-to-treat analyses will be used. Linear mixed models will be used to examine the relationship between group (peer, social support, wait list) and each outcome. Predictors in each model will be time, group, and their interaction. For all models, a random intercept will be included. The need for random slopes will be evaluated by examining model fit indices and testing the significance of the difference of the covariance estimate from zero. The peer group will be coded as the reference group to provide estimates and significance values for the difference between peer mentorship and each control condition.

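### The SAP's predictor list leaves diagnosis out of the models that pool anorexia, bulimia and binge eating disorder, which gives up a modest amount of precision

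*SAP*

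**What the plan says.** The SAP is one paragraph and covers every outcome with one model. On fixed effects: "Predictors in each model will be time, group, and their interaction". On random effects: "For all models, a random intercept will be included", with random slopes to be kept if fit indices and a test of the covariance estimate support them. On contrasts: "The peer group will be coded as the reference group to provide estimates and significance values for the difference between peer mentorship and each control". No baseline covariate is named. The protocol adds none, and its Interventions section says only that the research team will develop and run the randomization schema.

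The protocol uses diagnosis in several places:

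- Inclusion criterion 2 establishes it by EDA-5 at telephone screening, either currently or at entry to the most recent treatment course.
- Hyp 2b, whose endpoint is a BMI of at least 18.5, is restricted by it: "For individuals who meet criteria for current or past anorexia nervosa, individuals assigned to peer mentorship will be more likely to achieve or maintain". Hyp 2c is restricted to BN or BED.
- Mentors are matched on diagnostic subtype where possible, after randomization.
- Hyp 2a, by contrast, pools all three diagnoses on the EPSI, whose eight subscales include Restricting, Binge Eating and Purging (Assessment Instruments).

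On discharge timing, the Background says that "patients with EDs are at greatest risk for relapse in the first six month following discharge". Inclusion criterion 3 requires discharge within the past six months.

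**The concern.** Three disorders defined by different behaviours are analysed together on an instrument with subscales for those behaviours. If symptoms change at different rates in AN, BN and BED, diagnosis is a known source of slope variation that the planned models leave in the error. It is available for everyone before allocation, and neither design nor analysis is stated to guard against an uneven split.

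Three things are at stake: some precision in the peer-versus-control contrast, the credibility of that contrast if the arms differ visibly in diagnostic mix, and protection against choosing covariates after the data are seen. A fourth is conditional. The planned 100 enrolled and 80 completers imply 20% non-completion. If dropout depends on diagnosis, including it makes a missing-at-random assumption easier to defend.

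**Working it through.** **The plan's own figure.** The protocol requires 80 completers from 100 enrolled mentees: 80/(1 - 0.20) = 100, where the 20% is implied by the two numbers and not stated. No alpha, power, effect size or SD is given, so the 80 cannot be reproduced.

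**Inputs.** Three arms; 80/3 = 26.7 completers or 100/3 = 33.3 enrolled per arm (1:1:1 is an assumption). A diagnosis share p of 0.4 to 0.6 is also an assumption.

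**Chance imbalance between two arms.** 95% half-range = 1.96 × √[2p(1 - p)/n].

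- n = 27: p = 0.4 or 0.6 gives 1.96 × √(0.48/27) = 0.261; p = 0.5 gives 1.96 × √(0.50/27) = 0.267.
- n = 33: p = 0.4 or 0.6 gives 1.96 × √(0.48/33) = 0.236; p = 0.5 gives 1.96 × √(0.50/33) = 0.241.

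The range is therefore about ±24 to ±27 percentage points.

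**Precision of the slope contrast.** Let f be the share of the variance of estimated slopes that is true between-person variation, R² the share of that true variation explained by diagnosis, and q the number of diagnosis terms (1 for two levels, 2 for three). With 80 patients in three arms there are 80 - 3 = 77 error degrees of freedom on person-level slopes. Approximately,

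SE ratio = √[(1 - f·R²) × (1 + q/(77 - q - 1))]

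The second factor is 1 + 1/75 = 1.0133 for q = 1 and 1 + 2/74 = 1.0270 for q = 2.

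| f | R² | One term (q = 1) | Two terms (q = 2) |
|---|---|---|---|
| any | 0 | √1.0133 = 1.007 (+0.7%) | √1.0270 = 1.013 (+1.3%) |
| ½ | 5% | √(0.975 × 1.0133) = 0.994 (-0.6%) | √(0.975 × 1.0270) = 1.001 (+0.1%) |
| ½ | 20% | √(0.90 × 1.0133) = 0.955 (-4.5%) | √(0.90 × 1.0270) = 0.961 (-3.9%) |
| 1 | 5% | √(0.95 × 1.0133) = 0.981 (-1.9%) | √(0.95 × 1.0270) = 0.988 (-1.2%) |
| 1 | 20% | √(0.80 × 1.0133) = 0.900 (-10.0%) | √(0.80 × 1.0270) = 0.906 (-9.4%) |

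Simulation gave the same values for the cells it covered: R² = 0 and f = 1, R² = 20% in both columns; f = ½ for one term; and f = 1, R² = 5% for two terms.

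**How the covariate must enter.** A small simulation with a random intercept only (60 data sets, 27 per arm, 7 monthly visits, complete data) included both diagnosis and time since discharge. The SE of the time-by-group term was 0.0359 without covariates, 0.0359 with them as main effects, and 0.0367 with their time interactions added (0.0367/0.0359 = 1.022). Main effects lowered only the SE of the group main effect (0.2635 to 0.2329). This is expected: in these data no between-person slope variance exists to explain. A gain in the slope contrast therefore needs both true slope variation, which the SAP allows for through random slopes, and a diagnosis-by-time term.

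**The case against.** The strongest reply is that an unadjusted randomized comparison is valid and that this is a preliminary-efficacy trial. Differences in symptom level between diagnoses are absorbed by the random intercept. Only different trajectories matter, and the documents give no evidence of these. All of that stands. With no slope variance the gain is zero and the added terms cost slightly. Chance imbalance is already reflected in the standard error and does not bias the comparison on average.

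Three stronger readings are tempting and are not supported.

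- *That the trial records time since discharge and treats it as prognostic.* Criterion 3 documents a within-six-months check, and no listed instrument stores the date. The Background statement on relapse risk describes the window that every participant is inside at entry; it does not rank patients within it.
- *That the protocol calls diagnosis prognostic.* It uses diagnosis for eligibility, matching and the restriction of Hyp 2b and 2c. Its effect on EPSI trajectories is an inference from subscale content.
- *That adjustment is worth 5-25% more patients.* Applying 80/(1 - R²) gives 80/0.95 = 84 to 80/0.80 = 100, but only if R² refers to all observed change, measurement error included, and the lost degrees of freedom are ignored. That is a best case.

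Adding an AN versus BN/BED term to every model would also be wrong. It is constant or nearly so within Hyp 2b and 2c, and because eligibility covers current or past illness, a lifetime split would not classify someone with more than one diagnosis.

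**Conclusion.** The point holds for diagnosis, as a matter of efficiency and pre-specification, and does not affect validity. It applies to the models that pool diagnoses. The expected reduction in the SE of the peer-versus-control slope contrast is about 1-5% with a single diagnosis term, or from nothing to about 4% with three levels, assuming diagnosis explains 5-20% of true slope variance and half of the slope-estimate variance is true. About 10% is the upper limit. If diagnosis is uninformative the SE grows by roughly 1%. R², f, the allocation ratio and the diagnosis shares are all assumptions; none comes from the documents. The case for the change rests as much on fixing the covariate in advance, in a small trial with no stated stratification, as on the precision gained.

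**What to change.** Add to the SAP, before outcomes are examined by arm, wording such as: *Models that pool diagnoses (EPSI, quality of life, comorbid symptoms, cost) will also include the qualifying EDA-5 diagnosis for the most recent treatment course (AN, BN, BED) and its interaction with time as fixed effects.*

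Keep AN versus BN/BED out of the Hyp 2b and 2c models; a BN versus BED term may be used in 2c. If the discharge date asked about at screening is recorded, months since discharge and its interaction with time can be added in the same way. If it is not recorded, that part would need a new data item. State how time is coded.

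The diagnosis part needs no new data. With three levels it uses 2 + 2 = 4 fixed-effect degrees of freedom if time is linear, or 2 + 2 × 6 = 14 if baseline and the six monthly visits are categorical.
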